#### 9.4 Gender and Minority Accrual Estimates

The gender and minority distribution of the study population is expected to be:

Racial Categories	Ethnic Categories				Total
	Not Hispanic or Latino		Hispanic or Latino		
	Female	Male	Female	Male	
American Indian/ Alaska Native	0	0	0	0	0
Asian	12	9	0	0	21
Native Hawaiian or Other Pacific Islander	0	3	0	0	3
Black or African American	21	27	0	0	48
White	105	77	29	29	240
More Than One Race	0	0	0	0	0
Total	138	116	29	29	312

This distribution was derived from AAML0431

## 10.0 EVALUATION CRITERIA

### 10.1 Common Terminology Criteria for Adverse Events (CTCAE)

This study will utilize version 5.0 of the CTCAE of the National Cancer Institute (NCI) for toxicity and performance reporting. A copy of the CTCAE version 5.0 can be downloaded from the CTEP website

([http://ctep.cancer.gov/protocolDevelopment/electronic\\_applications/ctc.htm](http://ctep.cancer.gov/protocolDevelopment/electronic_applications/ctc.htm)).

Additionally, toxicities are to be reported on the appropriate case report forms.

Please note: 'CTCAE v5.0' is understood to represent the most current version of CTCAE v5.0 as referenced on the CTEP website (i.e., v5.02 and all subsequent iterations prior to version 6.0).

### 10.2 Response Criteria for Patients with Acute Myeloid Leukemia and Myelodysplastic Syndrome of DS

If the bone marrow sample used for the assessment of response is aplastic or severely hypocellular, the bone marrow aspirate and complete response assessment (including MRD) should be repeated every 7 to 21 days until a response evaluation can be made.

#### 10.2.1 Complete Response (CR)

The bone marrow is cellular with regenerating normal hematopoietic cells. There are < 5% blast cells by morphology and there is no evidence of extramedullary disease (EMD).

#### 10.2.2 Partial Response (PR)

If there is neither a Complete Response (CR) nor Refractory Disease (RD).

#### 10.2.3 Refractory Disease (RD)

Two consecutive bone marrow evaluations (separated by at least 2 weeks) that are at least moderately cellular and contain  $\geq 5\%$  leukemic blasts by morphology and MRD **or** evidence of extra-medullary disease at the end of Induction II. In patients with myelodysplastic syndrome, there are  $> 5\%$  malignant blasts.

#### 10.2.4 Relapse

Morphologic relapse after CR is defined as a reappearance of leukemic blasts in the peripheral blood or  $\geq 5\%$  blasts in the bone marrow not attributable to any other cause (e.g. bone marrow regeneration) after documented CR. In the setting of recent treatment, if there are no circulating blasts and the bone marrow contains 5% to 20% blasts, **a repeat bone marrow performed at least a week later is necessary** to distinguish relapse from bone marrow regeneration. Should local flow cytometric analyses suggest relapse (by the reappearance of a similar immunophenotype to the original leukemia) in the presence of <5% blasts, or  $\geq 5\%$  blasts in a regenerating marrow, **a repeat bone marrow(s) performed at least a week later is necessary** to confirm relapse by morphologic methods. In such instances the date of recurrence is defined as the first date that more than 5% leukemic blasts were observed in the marrow.

Cytogenetic relapse is characterized by reappearance of a cytogenetic or molecular abnormality after documented CR. A bone marrow examination performed at least a week later is necessary to confirm cytogenetic relapse.

Extramedullary disease relapse is defined as appearance of cytologically proven extramedullary disease after documented CR.

#### 10.2.5 Unevaluable

The bone marrow is aplastic or severely hypocellular (with any blast percentage). In this instance, bone marrow evaluation should be repeated every 7 to 21 days until a response determination can be made.

### 11.0 ADVERSE EVENT REPORTING REQUIREMENTS

#### 11.1 Purpose

Adverse event data collection and reporting, which are required as part of every clinical trial, are done to ensure the safety of patients enrolled in the studies as well as those who will enroll in future studies using similar agents.

#### 11.2 Determination of Reporting Requirements

Reporting requirements may include the following considerations: 1) the characteristics of the adverse event including the *grade* (severity); 2) the *relationship to the study therapy* (attribution); and 3) the *prior experience* (expectedness) of the adverse event.

Commercial agents are those agents not provided under an IND but obtained instead from a commercial source. In some cases an agent obtained commercially may be used for indications not included in the package label. In addition, NCI may on some occasions distribute commercial supplies for a trial. Even in these cases, the agent is still considered to be a commercial agent and the procedures described below should be followed.

Determine the prior experience Expected events are those that have been previously identified as resulting from administration of the agent. An adverse event is considered *unexpected*, for reporting purposes only, when either the type of event or the severity of the event is not listed in:

- *the current known toxicities for each commercial agent as provided in the Drug Information for Commercial Agents Used by the Children's Oncology Group posted on the COG website; or*
- *the drug package insert.*

#### Secondary Malignancy

A *secondary* malignancy is a cancer caused by treatment for a previous malignancy (eg, treatment with investigational agent/intervention, radiation or chemotherapy). A metastasis of the initial neoplasm is not considered a secondary malignancy.

All secondary malignancies that occur following treatment need to be reported via CTEP-AERS. Three options are available to describe the event:

- Leukemia secondary to oncology chemotherapy
- Myelodysplastic syndrome
- Treatment related secondary malignancy

Any malignancy possibly related to cancer treatment (including AML/MDS) should also be reported via the routine reporting mechanisms outlined in each protocol.

### **Second Malignancy**

A **second** malignancy is one unrelated to the treatment of a prior malignancy (and is **NOT** a metastasis from the initial malignancy). Second malignancies require **ONLY** routine reporting via CDUS unless otherwise specified.

### **11.3 Reporting of Adverse Events for Commercial Agents – via CTEP-AERS**

Expedited AE reporting must use CTEP-AERS (Adverse Event Expedited Reporting System), accessed via <https://eapps-ctep.nci.nih.gov/ctepaers>

Commercial reporting requirements are provided in Table B. The commercial agent(s) used in this study are listed in the front of this protocol immediately following the Study Committee roster.

- COG requires the CTEP-AERS report to be submitted within 7 calendar days of learning of the event.
- Use the NCI protocol number and the protocol-specific patient ID provided during trial registration on all reports.

**CTCAE term (AE description) and grade:** The descriptions and grading scales found in the revised NCI Common Terminology Criteria for Adverse Events (CTCAE) version 5.0 will be utilized for AE reporting. All appropriate treatment areas should have access to a copy of the CTCAE version 5.0. A copy of the CTCAE version 5.0 can be downloaded from the CTEP website at: [http://ctep.cancer.gov/protocolDevelopment/electronic\\_applications/ctc.htm](http://ctep.cancer.gov/protocolDevelopment/electronic_applications/ctc.htm).

### **Table B**

**Reporting requirements for adverse events experienced by patients on study who have NOT received any doses of an investigational agent on this study.**

### **CTEP-AERS Reporting Requirements for Adverse Events That Occur During Therapy with a Commercial Agent or Within 30 Days**

Attribution	Grade 4		Grade 5
	Unexpected	Expected	
Unrelated or Unlikely			CTEP-AERS
Possible, Probable, Definite	CTEP-AERS		CTEP-AERS

This includes all deaths within 30 days of the last dose of treatment with a commercial agent, regardless of attribution. Any death that occurs more than 30 days after the last dose of treatment with a commercial agent that can be attributed (possibly, probably, or definitely) to the agent and is not due to cancer recurrence must be reported via CTEP-AERS.

### 11.4 Routine Adverse Event Reporting

**Note:** The guidelines below are for routine reporting of study specific adverse events on the COG case report forms and do not affect the requirements for CTEP-AERS reporting.

The NCI defines both routine and expedited AE reporting. Routine reporting is accomplished via the Adverse Event (AE) Case Report Form (CRF) within the study database. For this study, routine reporting will include all toxicities reported via CTEP-AERS and all Grade 3 and higher non-hematologic Adverse Events, and all grades of the following cardiac Adverse Events: prolonged QTc interval and left ventricular systolic dysfunction.

### 11.5 Syndrome Reporting

Unless otherwise specified in this protocol, syndromes should be reported as a single event using the CTCAE term for the composite syndrome, and not as the individual events that make up the syndrome. For example, Tumor Lysis Syndrome should be reported under the composite definition rather than reporting the component events (hyperkalemia, hyperphosphatemia, hypocalcemia, hyperuricemia) separately.

## 12.0 RECORDS AND REPORTING

See the Case Report Forms posted on the COG web site with each protocol under “*Data Collection/Specimens*”. A submission schedule is included.

### 12.1 Clinical Data Update System (CDUS)

This study will be monitored by the Clinical Data Update System (CDUS). Cumulative CDUS data will be submitted quarterly to CTEP by electronic means. Reports are due January 31, April 30, July 31 and October 31. This is not a responsibility of institutions participating in this trial.

## 13.0 PATHOLOGY GUIDELINES AND SPECIMEN REQUIREMENTS

### 13.1 Diagnostic Specimen Requirements for Central Review

1. One Wright & Giemsa stained and 6 unstained bone marrow aspirate smears.
2. Flow cytometry report.
3. Bone marrow pathology report.
4. Cytogenetic report and reports for any molecular testing for chromosomal translocations
5. Results of a complete blood and differential count (manual or automated) obtained on the same day as the bone marrow aspirate
6. One H&E stained and 6 unstained sections of bone marrow core biopsy (if obtained).
7. One H&E stained and 6 unstained sections of bone marrow clot section (if available).
8. One Wright & Giemsa stained and 2 unstained peripheral blood smears (if available).
9. Specimen Transmittal Form.

For patients with myeloid sarcoma (chloroma), the following materials must also be submitted for central pathology review:

- 1) One H&E stained slide and 6 unstained recuts from the biopsy material of the myeloid sarcoma, if obtained. Slides must be sent from a representative block with remaining diagnostic material.
- 2) Immunohistochemistry stained slides that were used to establish the diagnosis (this is strongly recommended, but not required; these special stained slides will be sent back at the conclusion of review, if requested by contributor).
- 3) A copy of pathology report (including results of special stains, flow cytometry and cytogenetics, if performed).

[figure not shown]
Please label all materials for Central Review with the subject's COG identification number, the institutional surgical pathology identification number (SPID) and the block number from the corresponding report.

**The Biopathology Center will forward the materials to:**

#### 13.2 **Local Cytogenetic Analysis and Data Submission to Central Laboratory**

##### 13.2.1 Specimen Collection for Local Cytogenetics Analysis

Collect approximately 5 mL of bone marrow for cytogenetics in a sodium heparin tube (green top vacutainer) or utilize transport media provided by your cytogenetics laboratory. It is best to use the specimen from the first or second draw for cytogenetics analysis in order to capture the dividing abnormal cells. It is recommended that cytogenetics laboratories keep leftover cytogenetic pellets in order to evaluate equivocal results.

**Please note:** Peripheral blood (3-5 mL) collected in sodium heparin should be submitted as a back-up to the bone marrow when the marrow sample is suboptimal or unobtainable.

It is required that a specimen be sent to your institutional cytogenetics laboratory at study entry. Submission of an additional specimen is recommended at relapse, but is not required. A case will be considered normal when a +21, mosaic +21 or Robertsonian translocation is present. A case will be considered abnormal when an acquired clonal chromosomal abnormality is present, in addition to the constitutional +21, mosaic +21, or Robertsonian translocation.

#### 13.2.2 Data Submission to Central Laboratory Following Local Cytogenetics Analysis

Submit the following to one of the central COG Cytogenetics Laboratories listed below after completion of local cytogenetic studies:

- 1) COG Cytogenetics Reporting Form (CYTOGFRM FISHFRM.pdf available from Generic Forms on COG Web site).
- 2) If abnormal, two different abnormal karyotypes from each cell line.
- 3) If normal, two normal karyotypes.
- 4) If FISH was performed, please send the following:
  - a) Images to document the findings, and a
  - b) COG FISH Reporting Form (CYTOGFRM FISHFRM.pdf available from Generic Forms on COG web site).

Please send above materials by e-mail (preferably as a PowerPoint file) to the following COG Cytogenetics Laboratories:

[figure not shown]
WEST OF MISSISSIPPI RIVER  
(INCLUDE MINNESOTA AND  
WISCONSIN), AUSTRALIA, NEW  
ZEALAND, WESTERN CANADA

SEND TO:

A series of approximately 15 horizontal black bars of varying lengths, representing redacted e-mail addresses for laboratories in the West of Mississippi River region.

EAST OF MISSISSIPPI RIVER  
(EXCLUDE MINNESOTA AND  
WISCONSIN), EUROPE, EAST  
CANADA

SEND TO:

A series of approximately 15 horizontal black bars of varying lengths, representing redacted e-mail addresses for laboratories in the East of Mississippi River region, Europe, and East Canada.

## 14.0 SPECIAL STUDIES SPECIMEN REQUIREMENTS

### 14.1 Summary of Specimens

Study	Time points	Collection Details	Additional Details	Mailing Destination
MRD Required from all patients	→ Pre-treatment → End of Induction I → End of Induction II (High Risk Patients only)	2-4 mL of anticoagulated bone marrow in sodium heparin (green top tube).  For the Pre-Treatment sample only: If BM sample cannot be obtained, and the peripheral blood has at least 20% blasts, send 5 mL of blood in sodium heparin (green top tube).	Store at room temperature. Ship on the day of collection. If sample is stored for longer than 24 hours, add equal volume of RPMI medium. Do not freeze MRD samples. ( See Section 14.2 )	1 ([name]'s lab) Section 14.2.3
Banking of viable cells (Optional: Patient Consent Required)	→ Pre-treatment → End of Induction I → Relapse	3-10 mL bone marrow into a sterile syringe containing a sterile solution of preservative-free heparin.	Place in a 15 mL sterile conical centrifuge tube and add 5 mL of sterile RPMI-1640 with 20% fetal calf serum. If specimen is not shipped on the day of collection, store in a refrigerator until shipment. ( See Section 14.3 )	2 (Leukemia Biospecimen Bank at BPC) Section 14.3.3
GATA-1 mutation (Optional: Patient Consent Required)	→ Pre-treatment → End of Induction I	2-4 mL bone marrow into an EDTA containing tube (purple top).	If specimen is not shipped on the day of collection, store in a refrigerator until shipment. ( See Section 14.3 )	2 (Leukemia Biospecimen Bank at BPC) Section 14.3.3

## 14.2 Destination 1 (MRD for [name]'s Laboratory)

### 14.2.1 Forms

Utilize AML Specimen Transmittal forms specific for AAML1531.

### 14.2.2 Labeling and Packaging

- Label the tubes with COG ID number, date and time of collection, time point (include treatment cycle and day of cycle), and source of material (e.g., bone marrow).
- Specimens should be placed inside a leak proof biohazard envelope with absorbent material and then a pressure resistance Tyvek envelope.

## 14.3 Destination 2 (COG Leukemia Biospecimen Bank, BPC)

### 14.3.1 Forms

Utilize AML Specimen Transmittal forms specific for AAML1531.

### 14.3.2 Labeling and Packaging

- Ship at room temperature.
- Label the tubes with COG ID number, patient name, date of birth, date and time of collection, time point (include treatment cycle and day of cycle), and source of material (i.e., bone marrow).
- Specimens should be placed inside a leak proof biohazard envelope with absorbent material and then a pressure resistance Tyvek envelope as per IATA regulations.

## 14.4 Banking Specimens

If the patient consents, any specimens left over on this study after required tests are performed will be banked for future research studies, as detailed in [Section 14.1](#). Samples should be labeled and shipped as detailed in [Section 14.3](#).

## 15.0 DESCRIPTION AND ANALYSIS OF EXPLORATORY STUDIES

The exploratory studies detailed in this section are for research purposes only, and results will not be used to make clinical treatment decisions. **With the exception of the MRD results after Induction I**, all other results will not be obtained in real-time (but rather batched for retrospective review,) and results will not be returned to the treating physician.

Please note, if there is an inadequate amount of bone marrow for all studies, the studies should be prioritized in the following order:

1. Bone marrow for Minimal Residual Disease Testing (See [Section 14.2](#))
2. Bone marrow for *GATA1* (See [Section 14.3](#))
3. Bone marrow for viable cell banking (See [Section 14.3](#))

### 15.1 Exploratory Aims

15.1.1 To determine the extent to which elimination of HD Ara-C from treatment of standard risk DS AML decreases adverse events and resource utilization in children with DS. With amendment #4A, this exploratory aim is complete.

Comparison will be made to predecessor study AAML0431, which included treatment with HD Ara-C. Since the first cycle of induction therapy is identical in both studies, comparison will be made for the time interval from end of Induction I to the completion of protocol therapy. Specifically, we will determine if elimination of HD Ara-C from treatment of standard risk DS AML results in:

15.1.1.1 A significant decrease of the number of days per patient spent on protocol therapy compared to predecessor study AAML0431.

Subjects who are MRD negative following Induction I, will continue on Arm A for SR patients with the elimination of HD Ara-C. We hypothesize that the elimination of the cycle of HD Ara-C will result in overall shorter treatment duration by reducing the total number of cycles of therapy as well as less cumulative myelotoxicity that might contribute to delays in starting subsequent cycles. A two-sample t-test will be used to compare average number of days per patient spent on protocol therapy for standard risk patients on AAML1531 compared to patients treated on AAML0431.

15.1.1.2 A significant decrease of the average number of days of hospitalization per patient compared to predecessor studies AAML0431 and A2971.

We similarly anticipate that the duration of hospitalization throughout protocol therapy will be reduced. The number of days in hospital will be determined for patients treated on AAML1531 Arm A and compared with the predecessor study A2971. A2971 patients with DS AML less than 4 years of age stayed a mean of 35.1 days in hospital (standard deviation 18.9) after the start of Induction II through the remainder of protocol therapy. Data regarding days of hospitalization during protocol treatment were not collected for study AAML0431. These data, however, are available for a subset of patients who were

treated at centers contributing data to the Pediatric Health Information Systems (PHIS) database. Data from AAML0431 will be merged with PHIS resource utilization data as previously described. Based on this prior experience, approximately 40% of patients enrolled on AAML0431 will have PHIS data available. Two-sample t-test will be used to compare average number of days of hospitalization per patient for standard risk patients on AAML1531 compared to patients treated on AAML0431 and A2971.

15.1.1.3 A significant decrease of the number (per patient) and rate (per duration of treatment) of sterile site infections compared to the predecessor study AAML0431.

In addition, we hypothesize that the elimination of HD Ara-C will lead to less morbidity compared to patients whose treatment historically included this cycle. On the predecessor study, AAML0431, the greatest number of adverse events occurred during the administration of HD Ara-C (27.5% of the total reported), with 65% of adverse events classified as Grade 3 or greater (6.5% were Grade 4). These included Grade 3 or greater sterile site bacterial infection in 23% of patients and febrile neutropenia in 30% of patients, resulting in the need for continuous hospitalization. We anticipate fewer sterile site infections for patients with DS AML being treated on AAML1531 without HD Ara-C compared with the predecessor study, AAML0431, which included the use of HD Ara-C. The number (per patient) and rate (per duration of treatment) of sterile site infections of patients treated for DS AML on Arm A will be compared to AAML0431 after the start of Induction II. Poisson regression will be used to compare rate (per duration of treatment) of sterile site infections for standard risk AAML1531 patients with AAML0431 patients.

15.1.1.4 A significant decrease of resource utilization by AML treatment compared to the predecessor study AAML0431.

Given our anticipation of fewer sterile site infections and shorter hospitalization, we hypothesize that the elimination of HD Ara-C on AAML1531 will ultimately result in decreased resource utilization (after the start of Induction II on AAML1531 Arm A), as sepsis is the single most important factor determining length of stay and hospital costs in the treatment of children with leukemia. Resource utilization will be compared between patients on AAML0431 and AAML1531 at PHIS sites by comparing rates of inpatient resource utilization including antimicrobial usage, ICU level care resources, standard pharmaceutical supportive care measures, and blood products. PHIS adjusted inpatient costs will also be compared between patients enrolled on AAML0431 and AAML1531. These measurements of resource utilization and standardized costs will be compared between the current treatment protocol (Arm A, no HD Ara-C cycle) and predecessor study AAML0431, which included the use of HD Ara-C.

These data on duration of therapy, length of hospital admission and sterile site infections are routinely submitted for patients with AML. Analysis of these exploratory objectives is expected to measure potential gains made for SR DS AML patients by decreasing the numbers of adverse events through a reduction in treatment intensity.

**15.1.2 To compare feasibility and analytical characteristics of flow cytometry, PCR and targeted error-corrected sequencing of *GATA1* mutations as methods to detect MRD in DS AML (Exploratory aim 1.2.1)**

**Background.** *MRD*. The assessment of early response to treatment by measuring minimal residual leukemic disease (MRD) in the bone marrow has provided a new, independent and powerful prognostic marker for children with leukemia. In clinical practice, the blasts of acute lymphoblastic leukemia (ALL) can be detected by multi-dimensional flow cytometry based on patterns of surface and cytoplasmic proteins that are either different from normal hematopoietic cells or associated with a patient's specific leukemia. Alternatively, malignant lymphoblasts can be quantified at submicroscopic levels by DNA-based polymerase chain reactions designed to amplify an individual patient's clone-specific rearrangement of antigen receptor (immunoglobulin and T cell receptor) genes. In contrast, detection of MRD in acute myeloid leukemia (AML) relies predominantly on multi-dimensional flow cytometry due to the absence of widely prevalent, clone-specific molecular lesions. The blasts of AML in young children with Down syndrome (DS), however, typically contain somatic, clone-specific mutations of the gene encoding the hematopoietic transcription factor *GATA1* on the X chromosome. These mutations consist of short insertions, deletions and point mutations clustering within and adjacent to exon 2. As a result, measurement of MRD in DS AML is uniquely feasible both by multi-dimensional flow cytometry and DNA-based methods.

**Methods.** Multi-dimensional flow cytometry has the advantage that it can be performed rapidly, but its sensitivity and specificity is limited in DS AML. Of note, interpretation of flow cytometric MRD data in DS AML is complicated by the observation that normal bone marrow cells in DS may express patterns of surface markers that are absent from normal non-DS bone marrow ([name], personal communication). These patterns must not be confused with evidence of residual leukemia (when defined as marker pattern that is different from normal). DNA-based methods, such as quantitative real time PCR can detect individual patients' clone-specific *GATA1* mutations in exon 2 using either mutation-specific primers (and a shared probe) or a mutation-specific probes (and shared primers) with high sensitivity and specificity but can encounter limitations to feasibility due to constraints on the design of primers and probes in a short exon. Digital PCR technology, with its increased options for primer design, and massively parallel sequencing, which circumvents the constraints of designing mutation-specific oligonucleotide primers and probes, provide promising new approaches to the detect *GATA1* mutations and measure MRD in DS AML.

**Hypotheses.** We hypothesize that measurement of MRD in DS AML by digital PCR to detect clone-specific *GATA1* mutations is feasible and both more sensitive and specific than multi-dimensional flow cytometry. We hypothesize further that

measurement of MRD in DS AML by error-corrected sequencing (ECS) of exon 2 of *GATA1* to detect clone-specific mutations is as sensitive and specific as digital PCR but more cost-effective (since there is no need for mutation-specific primer and probe design). ECS has shown sensitivity for single base substitutions to 1:10,000, validated by digital PCR^61 and comparable to flow cytometry or RT-PCR.

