## 2.9

### **Interim Analysis of Patients Treated on the Standard Risk Arm**

According to the study analysis plan, an interim analysis of treatment outcomes for lack of efficacy on the Standard Risk (SR) arm (Arm A) was performed after 50% of the expected number of EFS events had been observed (after 8 of 16 events). Based on a model generated using data of SR patients in the historical control (predecessor study AAML0431) and the amount of follow-up available at the time of data cut off (30 June 2018), 2.4 EFS events were expected in SR patients compared to 8 EFS events observed. The projected 2-year EFS for SR patients on AAML1531 is significantly lower than on AAML0431 (85.6% compared to 93.5%, p 0.0002). As of October 5, 2018, 9 of 109 SR patients on AAML1531 have experienced a relapse at 136 to 327 days after study entry. Four of these relapses occurred on therapy (1 during Intensification I, 3 during Intensification II) and 5 during the first 6 months of follow up after completion of protocol therapy. Of the 9 relapsed SR patients, 8 have died.

These data show lack of sufficient efficacy of AAML1531 protocol therapy for SR patients. Based on this information, post-Induction I treatment on the SR Arm A of AAML1531 was permanently closed.

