## 9.0 STATISTICAL CONSIDERATIONS

### 9.1 Statistical Design

This study is a non-randomized study of children with DS and AML. The primary endpoint of interest will be the event-free survival (EFS) from the end of Induction I to failure to achieve remission at the end of Induction II, relapse, occurrence of a second malignancy or death.

Other outcome measures will include average total number of days per patient spent on protocol therapy, early death rates, overall survival from on study, treatment related mortality, relapse risk, percentage of patients experiencing Grade 3 or higher toxicity, time to count recovery, duration of hospitalization, and infection rates.

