## 9.3 Statistical Analysis Methods

### 9.3.1 Analysis Plan

The Kaplan-Meier method will be used to estimate 2-year EFS from the end of Induction I along with 95% log-minus-log transformed confidence limits separately for HR and SR patients at end of Induction I. To compare the Kaplan Meier estimate of 2-year EFS (KM2) with fixed values, we will use the test statistic  $\frac{\ln(-\ln(\text{KM2})) - \ln(-\ln(0.935))}{\text{Estimated SD} [\ln(-\ln(\text{KM2}))]}$  for SR and  $\frac{\ln(-\ln(\text{KM2})) - \ln(-\ln(0.76))}{\text{Estimated SD} [\ln(-\ln(\text{KM2}))]}$  for HR patients and compare these with a standard normal distribution.

\* Updated with Amendment #4A

AAML1531 was temporarily closed to accrual on October 1, 2018, due to results of an interim analysis identifying a significantly lower EFS for SR patients than that expected based on comparative data from AAML0431. Post-Induction I treatment on the SR Arm A was permanently closed on October 18, 2018. All patients enrolled prior to amendment #4A who were assigned to the SR arm were to be taken off protocol therapy but may stay on study. These SR patients enrolled prior to amendment #4A who are taken off protocol therapy due to the closure of treatment on the SR arm will be censored in future EFS analysis at the time they were taken off protocol therapy. Patients enrolled after amendment #4A who are assigned to the SR arm will be removed from study and continue treatment off protocol per standard of care. No further data will be collected on these patients.

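### Arm A's closure has an analysis rule for EFS only; without one for days on therapy, hospital days and infections per patient, courses stopped by the closure would count as short courses

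*Combined protocol and SAP*

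**What the plan says.** Section 9.3.1, as updated with Amendment 4A, separates two dates. Accrual paused on 1 October 2018, and post-Induction I treatment on Arm A closed permanently on 18 October 2018. SR children enrolled before the amendment "who were assigned to the SR arm were to be taken off protocol therapy but may stay on study". Their only analysis rule is that they "will be censored in future EFS analysis at the time they were taken off protocol therapy".

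Section 15.1.1 describes what dropping high-dose cytarabine was expected to save. It states that "comparison will be made for the time interval from end of Induction I to the completion of protocol therapy". Three comparisons matter here:

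- **15.1.1.1, treatment days:** "A two-sample t-test will be used to compare average number of days per patient spent on protocol therapy", with the SR children of AAML1531 on one side and AAML0431 patients on the other.
- **15.1.1.2, hospital days:** a two-sample t-test of mean days per patient, against AAML0431 and A2971.
- **15.1.1.3, sterile site infections:** a number per patient and a rate per duration of treatment. Poisson regression is named for the rate only.

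None of these has an exclusion, a censoring rule or a cut-off date for children stopped by the closure. Section 15.1.1 adds: "With amendment #4A, this exploratory aim is complete". Section 9.1 still lists, among the other outcome measures, "average total number of days per patient spent on protocol therapy, early death rates, overall survival from on study", and further on duration of hospitalization and infection rates.

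**The concern.** The closure was administrative for a child who was still responding. That child's Arm A course is incomplete; it is not a short course. A t-test on per-patient means cannot tell the two apart. A child stopped after one of the four remaining cycles contributes about a quarter of the planned days, and correspondingly fewer hospital days and fewer chances of infection.

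On these three measures the error runs one way, making Arm A look lighter than a completed course would be. Section 15.1.1 sets out to measure the gain from reduced treatment intensity, so the bias would fall on the quantity being estimated. The plan recognises the problem for EFS and does not carry it over to these outcomes.

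**Working it through.** **Plan's own figure.** No power or effect size is stated for the exploratory comparisons. The only design figure for Arm A is 95% power in Section 9.2 (93.5% against 87%, 200 patients, one-sided 10%). An exact binomial test rejecting at 19 or more events of 200 has power 94.8% (type I error 6.3%), so it reproduces. It does not bear on the issue below.

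**Inputs from the documents**
- AAML0431 median cycle lengths (Section 2.4): high-dose cytarabine cycle 42 days; the other post-Induction I cycles 32, 34, 35 and 35 days.
- Sterile site infections by cycle, % of patients (Table 2): 22.6 in the high-dose cycle; then 11.3, 8.8, 12.7 and 8.4.
- 109 SR patients on 5 October 2018 (Section 2.9).
- SR share 83%, with up to 3% ineligible and up to 3% off therapy after Induction I (Section 9.2): 0.83 × 0.94 = 0.78.
- Planned accrual 60 per year (Section 9.2). Enrolment of 143 on 22 October 2018 and 222 on 25 August 2020 implies about 43 per year, though that period follows the closure.
- A2971 hospital days: mean 35.1, SD 18.9 (15.1.1.2); n = 132 (Section 2.5), about 126 without the six older children (Section 2.10.3).

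**Assumptions, not in the documents.** Arm A cycles last as long as the AAML0431 medians. Children were spread evenly through treatment at closure, so each lost half on average. Accrual before closure was 30 to 60 per year; 30 is a deliberately low bound.

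**Treatment days**
- AAML0431 after Induction I: 42 + 32 + 34 + 35 + 35 = 178. Full Arm A: 178 − 42 = 136. Untruncated saving: 42.
- Number cut short = accrual × 0.78 × 136/365. Mean loss per SR child = fraction cut short × 136/2.

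| Accrual per year | Cut short | Share of 109 | Mean loss (days) | Apparent saving (days) | Too large by |
|---|---|---|---|---|---|
| 30 | 8.7 | 8% | 5.4 | 47.4 | 13% |
| 43 | 12.5 | 11.5% | 7.8 | 49.8 | 19% |
| 60 | 17.4 | 16% | 10.9 | 52.9 | 26% |

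**Infections per 100 patients** (cycle percentages summed as an approximate count)
- AAML0431: 22.6 + 11.3 + 8.8 + 12.7 + 8.4 = 63.8. Full Arm A: 41.2. Difference: 22.6.
- At 8% cut short: loss 0.08 × 41.2/2 = 1.6, difference 24.2. At 16%: loss 3.3, difference 25.9.

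**Infection rate per 100 treatment days.** Full Arm A: 41.2/136 = 0.303. Allocating infections cycle by cycle gives 0.317 among the truncated children alone, so the pooled rate hardly moves.

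**Hospital days, with no true difference from A2971** (stay assumed proportional to treatment received)
- Spurious drop = fraction × 35.1/2: 1.8 days at 10% cut short, 2.8 days at 16%.
- SE = 18.9 × √(1/109 + 1/126) = 2.47.
- A nominal two-sided 5% test (sidedness is not stated in the plan) would reject about 10–11% of the time at 10% cut short and about 18–21% at 16%. Each range spans simulation and normal approximation.

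**The case against.** The strongest reply is that the aim is finished. Section 15.1.1 declares it complete, Section 1.2 no longer lists it, Section 15.0 says exploratory results do not guide clinical treatment decisions, and Arm A will not reopen. That limits the stakes. It does not settle the analysis, because the statement of completion names no analysis set or cut-off, and Section 9.1 still lists these outcomes.

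A second reply is that a window running to completion of protocol therapy implies completers only. The text does not say so. Near the closure date such a rule would also keep faster courses and drop slower ones, so it would not remove the bias.

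A third reply stands: the infection rate per duration of treatment already adjusts for exposure, and it is the only infection measure with a named test.

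A reader might infer more than the documents support:

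- **That the saving has in fact been overstated.** The documents do not report how stopped children were counted or how many there were.
- **That relapses on therapy add bias the same way.** Section 2.9 reports "Four of these relapses occurred on therapy (1 during Intensification I, 3 during Intensification II"), so three of the four came in the last cycle. AAML0431 had 14 relapses, which could also shorten courses there.
- **That the comparator, not limited to MRD-negative AAML0431 children, favours Arm A.** MRD-positive children did worse (2-year EFS 76% against 93%). Early stops among them would shorten the comparator course and understate Arm A's saving. The net direction is not established.
- **That overall survival and relapse risk need the same censoring.** Following survival regardless of later therapy is conventional, so a closure-censored version is a preference.

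**Conclusion.** The point holds as a gap with a known direction and an uncertain size. As worded, the comparisons of mean treatment days, mean hospital days and infections per patient include children whose Arm A course was ended by the closure, and counting those courses as they stand would overstate the reduction. With 8% to 16% of 109 children cut short, a 42-day saving would read as about 47 to 53 days, and an infection difference of 22.6 per 100 patients as about 24.2 to 25.9.

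These figures rest on assumed accrual, AAML0431 cycle lengths and an even spread through treatment; the sponsor can replace them with the actual count. The 42 days is itself a reference value, since 15.1.1.1 also expects fewer delays between cycles. The aim is exploratory, but the correction is inexpensive and should be made before these comparisons are reported or relied on.

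**What to change.** In Section 15.1.1, and for the same outcomes in Section 9.1, state how children stopped by the closure are counted, using one of two rules:

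1. **Opportunity to complete.** Limit the per-patient comparisons to SR children who started Induction II early enough to have been able to finish Arm A before 18 October 2018. Define the set by start date, not by whether the child finished. Allow more than the 136-day sum of medians, because Table 2 shows individual cycles running well beyond them.
2. **Closure as censoring.** Estimate restricted mean days on therapy with closure censored. Give hospital days and infections per cycle started or per treatment day.

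Under either rule, report stops for relapse or death separately in both studies, and state the number of children on Arm A treatment at closure. Keep the Poisson infection rate as it is.

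As a sensitivity analysis, also compare with AAML0431 children who were MRD-negative (< 0.05%) where MRD is available. That is 125 of 146 tested, out of 205 (125/205 = 61%), which is too large a loss for the main comparison.

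The cost is somewhat fewer patients, a less favourable apparent saving and minor programming. The re-analysis uses data already in hand.
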